Ablative fractional carbon dioxide (CO₂) lasers are commonly used to improve the appearance of both conditions, either alone or through laser-assisted drug delivery.⁹⁻¹¹ While the mechanism is not completely understood, ablative fractional laser alone may induce MMPs to help remodel and normalize both collagen and elastin.¹¹

In this study, we seek to evaluate the effects of ablative fractional CO₂ laser treatment on the redistribution/regeneration of collagen on the clinical, microscopic, and molecular profiles hypertrophic scars and scleroderma.

Study design

A prospective cohort study of 10 subjects with hypertrophic scars and 10 subjects with scleroderma.

Analysis of Skin Samples

Optional skin samples will be used to test the hypothesis that fractional laser treatment can improve the clinical appearance of scars and scleroderma.

Skin will be sampled using four 3 mm-punch biopsies. Biopsies will be obtained from the treated lesion (1) and perilesional healthy skin (1) during the first and during the post-procedural visit. Skin biopsies will be optional for scleroderma subjects.

Using histopathological analysis, microscopic and immunohistochemical tissue effects between treatment arms will be compared.

The study will take place at MGH's Clinical Unit for Research Trials & Outcomes in Skin (CURTIS) at [name] or Translational Clinical Research Center (TCRC) on the 12th floor of the White Building.

III. Aims

The aims of this study are:

- To determine the efficacy of ablative fractional laser in clinical improvement of hypertrophic scars and scleroderma.

IV. Subject selection

Subjects will be screened to determine if they meet all the eligibility criteria specified below.

a. Inclusion Criteria

1. Subject must be able and willing to provide written informed consent and comply with the requirements of the study protocol;
2. In good general health, based on answers provided during the screening visit;
3. Any gender and any Fitzpatrick skin type;
4. Age equal to or greater than 18 years old;
5. Subjects in the hypertrophic scar branch must have at least one extragenital hypertrophic scar (defined as abnormal proliferation of scar tissue that forms at the site of cutaneous injury and does not regress and grows beyond the original margins of the scar) at least 4cm in length for scar treatment;
6. Subjects in the scleroderma branch must have eligible extragenital lesions; large enough to treat;

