approved by the IRB/Partner's HRC and is the most current version. If a new version of the consent form is approved by the IRB/Partner's HRC while a subject is still participating in the study, then the Investigator will inform the subject of the changes and, if the subject agrees to continue study participation, they should sign the updated form.

Electronic informed consent will be obtained prior to performance of any protocol-specific procedures.

c. Subject selection

Ten subjects with one or more hypertrophic scars and ten subjects with scleroderma will be recruited for this study. Each subject will undergo an biopsy of perilesional normal-appearing skin adjacent to lesion to be treated (scar or scleroderma) and an optional biopsy of the treated side at their final visit. Biopsies will only be optional for scleroderma subjects.

IV. Study Procedures

a. Study Visits and Procedures

Baseline Assessment (Phone Call/In-Person Visit)

The baseline/consent assessment will be done in-person or phone call upon physicians discretion. At the baseline visit, eligibility criteria, including a review of medical history and medications, and detailed information about the study will be reviewed. Informed consent will be obtained, if the subject desires to proceed with the study.

Trial treatment Visit 1

Once consented, range of motion assessment (non-facial scleroderma), Mouth Handicap in Systemic Sclerosis scale (facial scleroderma) and Modified Vancouver Scar Scale (hypertrophic scars)(Appendix 2) will be used to assess lesions. Medical photography of the lesions and urine pregnancy test (for female subjects of childbearing potential) will be obtained prior to treatment. OCT imaging and three-dimensional imaging (Cherry Imaging) may also be performed on select consented subjects. The subject will be questioned about itch and pain in the area that will be treated.

Two 3 mm-punch biopsies will be obtained, one from perilesional normal-appearing skin adjacent to treated lesion (scar or scleroderma), and one from skin treated with laser. Biopsies will be optional for scleroderma subjects.

The subject will be anesthetized with 23% lidocaine, 7% tetracaine topical numbing for 30 minutes to one hour, which is standard of care in laser clinic.

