Once the subject has been anesthetized, they will undergo laser treatment. The entire lesion will be treated with Ultrapulse CO₂ laser DeepFX an energy level between 20 mJ-50 mJ and 5%-10% density, 1-2 passes. The area to be treated will not exceed 20cm. Vaseline will be applied evenly with a gloved hand on the entire lesion following the procedure.

Trial treatment Visit 2 (1 month after treatment visit 1)

The treated lesion(s) will be evaluated clinically for any potential adverse events and urine pregnancy test (for female subjects of childbearing potential) will be obtained prior to treatment. Each area of scar or scleroderma will be marked with a surgical marker based on photographs from the previous visit to ensure the treatment area is consistent. Medical photography of the lesion and urine pregnancy test (for female subjects of childbearing potential) will be obtained prior to treatment. OCT imaging may also be performed on select consented subjects.

The subject will be anesthetized with 23% lidocaine, 7% tetracaine topical numbing for 30 minutes to one hour, which is standard of care in laser clinic. Once the subject has been anesthetized, they will undergo laser treatment. the lesion will be treated with Ultrapulse CO₂ laser DeepFX, an energy level of 20 mJ-50 mJ and 5%-10% density, 1-2 passes. The area to be treated will not exceed 20cm. Vaseline will be applied evenly with a gloved hand on the entire lesion following the procedure.

Trial treatment Visit 3 (1 month after treatment visit 2)

The treated lesion(s) will be evaluated clinically for any potential adverse events and urine pregnancy test (for female subjects of childbearing potential) will be obtained prior to treatment. Each area of scar or scleroderma will be marked with a surgical marker based on photographs from the previous visit to ensure the treatment area is consistent. Medical photography of the lesion and urine pregnancy test (for female subjects of childbearing potential) will be obtained prior to treatment. OCT imaging may also be performed on select consented subjects.

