This device is not FDA approved. However, it's been safely used in over 1000 research participants so far. OCT imaging is performed spectral-domain OCT scanner TELESTO II (Thorlabs Inc., Newton, New Jersey). It operates at a central wavelength of 1,300 nm with an output power of 2.2 mW with continuous wave exposure of approximately 30 seconds per image, non-pulsed. Using a lens with an optical lateral resolution of 13 μm (LSM03, Thorlabs Inc.), we acquire images with an oversampling factor of 2 \times leading to voxel sizes of 6.5 \times 6.5 \times 3.5 μm^3 and a field-of-view (FOV) of 6 \times 6 \times 3.5 mm³ (length \times width \times depth), acquired at an A-Scan rate of 76 kHz.

The imaging data is further processed and analyzed by custom made software tools implemented in MATLAB 2016b (MathWorks Inc). All OCT image data files will be labeled with the study subject number assigned to each subject upon consent. No identifying information will be used in labeling the image data files and the files will be stored on Partners OneDrive.

The OCT imaging system will be cleansed with 70% isopropyl alcohol wipe in the subject's presence prior to perform any imaging procedure. The subject's lesion at the intended OCT imaging sites will be cleansed with 70% isopropyl alcohol prep and allowed air dry thoroughly. A z-spacer (OCT-Imm03, ThorLabs, Inc., Newton, NJ) will be attached to the OCT probe and glycerol will be utilized for optical coupling (immersion) between the OCT spacer and the skin. The acquisition and saving time per image will be less than 1 minute. If study staff operating the OCT imaging device decide the images are of too low quality or contain artifacts that would affect analysis, this procedure may be repeated on an area of the skin within close proximity to the original imaging location but at least 2-3 cm away from the original location. After finishing the OCT imaging procedures, the z-spacer will be detached and cleansed with 70% isopropyl alcohol wipe then allowed to air dry thoroughly prior to next use.

Skin biopsies

Two skin biopsies will be obtained at visit 1 and at the post-procedural visit of perilesional normal-appearing skin adjacent to treated lesion (scar or scleroderma) and laser treated lesional skin. This will result in up to four biopsies per subject over the course of this study. Biopsies are optional for scleroderma patients only.

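### The biopsy plan contradicts itself on whether an untreated lesional sample is taken, how many samples there are and who may decline, and its between-arm histology comparison cannot show a laser effect

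*Combined protocol and SAP*

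**What the plan says.** **Visit 1 lesional sample.** Study Procedures, Trial treatment Visit 1, takes one perilesional biopsy "and one from skin treated with laser. Biopsies will be optional for scleroderma subjects". The Skin biopsies section uses one description for both visits: perilesional skin "and laser treated lesional skin". Within Visit 1, the biopsy paragraph comes first, then topical anaesthesia, then "Once the subject has been anesthetized, they will undergo laser treatment. The entire lesion will be treated". Photography and the pregnancy test are expressly tied to the period before the laser ("will be obtained prior to treatment. OCT imaging and three-dimensional imaging (Cherry Imaging) may also be performed on select consented subjects"). The biopsy is not.

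**Schedule.** Section II, Analysis of Skin Samples, says "Skin will be sampled using four 3 mm-punch biopsies" and then "Biopsies will be obtained from the treated lesion (1) and perilesional healthy skin (1) during the first and during the post-procedural visit". Section V.c gives each subject one perilesional biopsy "and an optional biopsy of the treated side at their final visit".

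**Who may decline.** Section II opens by calling the skin samples optional without naming a condition, and later makes them optional for scleroderma. V.c attaches the option to each subject's treated-side sample, and its next sentence restricts it to scleroderma. The Post-procedural visit and Skin biopsies sections restrict it to scleroderma only.

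**Planned comparison.** Section II says "microscopic and immunohistochemical tissue effects between treatment arms will be compared". The design is 10 subjects with hypertrophic scars and 10 with scleroderma, all given the same laser treatment. Section VII specifies a test for the PGA only.

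**The concern.** Section II says the study will look at laser effects on the microscopic and molecular profile as well as the clinical one. The histology section lists stains for collagen, elastic fibres, vessels and nerve fibres. Measuring change in these needs lesional tissue from the same subject before any laser and after the last session.

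Staff who follow the Visit 1 wording literally would sample the lesion after the first laser exposure. The later comparison would then set freshly lasered tissue against tissue one month after the third session. Staff who follow V.c would take no lesional sample at Visit 1. In either case the untreated baseline cannot be recovered later, and subjects would have had punch biopsies that do not answer the question.

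The comparison has its own fault, which does not depend on biopsy timing: no arm differs from another in treatment.

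**Working it through.** **The plan's own figures.** Section VII states 10 subjects per condition for a power of 0.8 on the PGA. A one-sample, two-sided t test at 0.05 with a difference of 1 point and an SD of 1 point has 9 degrees of freedom and noncentrality 1 × √10 = 3.16. Its power is 0.803, against 0.748 with 9 subjects. The figure reproduces and involves no biopsy data. The ceiling of four biopsies per subject also reproduces: 2 samples × 2 visits = 4.

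**Sections side by side.**

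| Section | Visit 1 | Final visit | Optional for |
|---|---|---|---|
| II, Analysis of Skin Samples | lesional 1, perilesional 1 | lesional 1, perilesional 1 | unrestricted at the opening; scleroderma later |
| V.c | no lesional sample mentioned | treated-side 1 (one perilesional sample in all, not clearly dated) | each subject, then scleroderma only |
| Trial treatment Visit 1 | perilesional 1, laser-treated 1 | – | scleroderma |
| Post-procedural visit | – | perilesional 1, lesional 1 | scleroderma only |
| Skin biopsies | perilesional 1, laser-treated lesional 1 | perilesional 1, laser-treated lesional 1 | scleroderma only |
| Remuneration | higher payment if biopsied | higher payment if biopsied | not stated |

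The payment terms fit biopsies at both visits: $200 + $50 + $50 + $200 = $500, the stated maximum. V.c is the only outlier on schedule.

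**Specimens.** Under the four-biopsy schedule, scars give 4 × 10 = 40 and scleroderma gives 0 to 4 × 10 = 40, so 40 to 80 in all. Visit 1 lesional samples number 10 plus 0 to 10. Under V.c the maximum is 2 × 20 = 40.

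**Pairs of untreated and treated lesional skin, assuming no dropout.**

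- Four-biopsy schedule, Visit 1 sample before the laser: 10 scar + 0 to 10 scleroderma = 10 to 20.
- Four-biopsy schedule, Visit 1 sample after the laser as worded: 0.
- V.c taken as the full schedule: 0.

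If the unrestricted option in the opening of Section II governed, even the first reading would guarantee no scar pairs. The range would be 0 to 10 for each condition.

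**What a between-arm comparison estimates.** Suppose *arms* means the two conditions. Write the mean lesional change as C₁ in scars and C₂ in scleroderma. Comparing changes estimates C₁ − C₂, which is zero whenever the two conditions respond equally, however large the response. Comparing final values adds the baseline difference between two diseases. Neither quantity is the change under laser within a condition.

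**The case against.** The strongest reply is that the Visit 1 sample is plainly meant to precede the laser. The visit text runs biopsy, anaesthesia, laser. The protocol also uses *treated* to identify a site before any laser is given: Section II does so for the first visit, and the Visit 1 sentence locates the perilesional sample beside the treated lesion. The phrase in the Skin biopsies section has to serve two visits at once. Subjects lasered in the past six months are excluded. This stands as the better reading. It does not remove the defect, because no sentence fixes the timing, and nearly the same words at the final visit must mean tissue that has been lasered.

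A second reply is that V.c is a lone summary sentence against several consistent sections and the payment terms, and that its own next sentence restricts the option to scleroderma. That also stands. A reader might infer that biopsies are optional for everyone; the documents do not establish that, and most of the text says otherwise. The conflict remains, since V.c and the opening of Section II say something different.

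A third reply is that Section VII uses *treatment arm* for what appear to be the two conditions. On that reading a comparison can be made. A reader might infer that the biopsy wording makes it impossible, but the two matters are unrelated. The difficulty is that a contrast between conditions does not isolate the laser effect, and self-selection among optional scleroderma biopsies would weaken it further.

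Finally, Section III lists one aim, clinical improvement, and the primary outcome is the PGA. That limits the importance of the point.

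**Conclusion.** The histology plan is internally inconsistent on timing, schedule and optionality, and its stated comparison does not match the design. The size is 10 scar lesional pairs plus 0 to 10 scleroderma pairs, which fall to zero under two of the three readings. These counts assume full enrolment and no dropout, and the 10 scar pairs assume that scar subjects may not decline.

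A reader might go further and conclude that the study has no untreated lesional baseline. The documents do not support that: the order of the Visit 1 text points to a pre-laser sample, and the loss follows only if the literal wording or V.c is acted on. Nor does the point reach the primary result, since the PGA sample size and test use no tissue data. It is a correction worth making before biopsies are taken, confined to a non-primary outcome.

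**What to change.** 1. Reconcile Section II, V.c, Trial treatment Visit 1, Post-procedural visit and Skin biopsies so that one biopsy schedule and one optionality rule for each condition apply throughout.
2. State when the Visit 1 lesional sample is taken relative to the laser. Only a pre-laser sample can serve as the untreated baseline.
3. Replace the between-arm comparison with a paired within-subject contrast, reported separately by condition: lesional final minus lesional Visit 1. The perilesional change can be an optional reference, for example (lesional final − lesional Visit 1) − (perilesional final − perilesional Visit 1). The simpler contrast is a reasonable main one with about 10 subjects: if the four values had equal variance σ² and were uncorrelated (an assumption), subtracting the perilesional change would raise the variance from 2σ² to 4σ². There is no untreated lesion at follow-up, so the result should be described as change under treatment.
4. Report how many subjects in each condition contribute a pair.

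The cost is a wording amendment and one analysis sentence. No biopsies are added relative to the four-biopsy schedule. Relative to V.c, that schedule would mean up to two more per subject, so the consent text should be checked against whichever schedule is adopted.

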7. Willing to sun protect treated area for the duration of enrollment in the study and 1 year after treatment.

b. Exclusion Criteria

1. Participation in another investigational drug or device clinical trial in the past 30 days;
2. Are pregnant or lactating;
3. Use of any prescription or in-clinic medications or treatments, such as intralesional corticosteroids or excision, on the eligible scars/scleroderma in the previous 3 months;
4. History of allergic reaction to topical or local anesthesia;
5. Regular intake of high doses of anti-inflammatory drugs (aspirin >81 mg/day, ibuprofen, corticosteroids, etc.) or high and/or non stabilized doses of immunosuppressive drugs;
6. Clinically significant abnormal findings or conditions which might, in the opinion of the Investigator, interfere with study evaluations or pose a risk to subject safety during the study;
7. Laser treatment in past six months;
8. History of poor wound healing.

c. Source and Recruitment of Subjects

The study will be posted on the Partner's clinical research web page (Rally), around the hospital, and outpatient clinics (treating scars, scleroderma, or morphea) to reach an economically and socially diverse population.

V. Subject Enrollment

a. Method of Enrollment

All subjects who electronically sign an informed consent form (ICF) and are screened will be documented on a screening log. All subjects who qualify at the screening visit and who are enrolled in the study will be documented on the enrollment log. A note will be made in the source documentation verifying that the subject has willingly signed the ICF prior to participation in any study procedures. All randomized subjects will receive a subject number.

b. Informed Consent Form (ICF)

A licensed physician investigator or sub-investigator will inform the potential study subject of all aspects of the study and answer their questions. If the subject agrees to be a study subject, they will document consent in electronic form by signing an online ICF via Adobe eSign. Subjects who need more time to decide whether they would like to participate will have access to the electronic consent form and will call if they are interested in participating in the study.

The investigator is responsible for using a consent form that has been

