The subject will be anesthetized with 23% lidocaine, 7% tetracaine topical numbing for 30 minutes to one hour, which is standard of care in laser clinic. Once the subject has been anesthetized, they will undergo laser treatment. The entire lesion will be treated with Ultrapulse CO₂ laser DeepFX, an energy 20 mJ-50 mJ and 5%-10% density, 1-2 passes. The area to be treated will not exceed 20cm. Vaseline will be applied evenly with a gloved hand on the entire lesion following the procedure.

Post-procedural visit (final visit, 1 month after treatment visit 3)

One-month after the last treatment The subject will be questioned about itch and pain in the treated area. Range of motion assessment (non-facial scleroderma),

Mouth Handicap in Systemic Sclerosis scale (facial scleroderma) and Modified Vancouver Scar Scale (hypertrophic scars) (Appendix 2) will be used to assess lesions. Lesion marked with surgical marker. Additional medical photography and two 3 mm-punch biopsies will be obtained, one from perilesional normal-appearing skin adjacent to treated lesion (scar or scleroderma), and one from lesional skin treated with laser. Biopsies are optional for scleroderma subjects only. OCT imaging and three-dimensional imaging (Cherry Imaging) may also be performed on select subjects.

Clinical assessment

Clinical photographs taken pre-treatment and post-treatment will be compiled and reviewed in blinded fashion by at least one dermatologist using the Physician's Global Assessment, a widely used scale from the existing literature to determine clinical change from baseline. We will use the Mouth Handicap in Systemic Sclerosis¹ scale for assessing facial scleroderma. For non-facial scleroderma, we will evaluate range of motion of the joint by assessing flexion, extension, supination, and pronation using a goniometer². All scars, facial and non-facial, will be assessed using the Modified Vancouver Scar Scale³.

Cherry Imaging Photography

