We will be using an approved, outside vendor (Forte Research) to make these payments via a reloadable credit card-based system, called Forte Payments. This secure system is similar to a gift card or credit card. If subjects are paid by this system, they will be given a Forte Payments Via card (which is just like a debit card) when subjects enroll in the study. Once the card is activated, the study team will add a payment after each paid visit completed by the subjects. The payment should be available within one (1) business day. Research staff will not know where subjects spend the money. Subjects may use the card anywhere Visa cards are accepted, such as at a grocery store.

We will need to collect subjects' Social Security number in order to make these payments, and it will be shared securely with the company that runs the card-based system. Payments like this are considered taxable income. If subjects receive more than \$600, the payment will be reported to the IRS as income by the hospital.

VII. Biostatistical Analysis

In order to detect a difference of one point assuming a standard deviation of one point on the primary clinical outcome measure, Physician's Global Assessment of Clinical Condition (PGA) scale (a numerical scale from 0-6), a sample size of 10 subjects per condition (10 for scars, 10 for scleroderma, 20 total) is required to achieve a power of 0.8. A student's t test, one sample, two-sided, will be used to determine if any significant statistical difference is present between the clinical response of each treatment arm using the absolute difference between the pre- and post-treatment PGA. A p-value of less than 0.05 is considered statistically significant.

VIII. Risks and Discomforts

There is a potential risk of loss of privacy. We will protect privacy by labeling samples and information only with a code, and keeping the key to the code in a password protected database.

Potential risks of the skin punch biopsy include allergic reaction to the anesthetic, bleeding, infection, poor wound healing, pain, hyper or hypopigmentation and scarring.

Possible risks of fractional laser surgery include pain, scarring, infection, abnormal wound healing, hyper or hypopigmentation.

Possible side effects of topical 23% lidocaine, 7% tetracaine include redness, mild burning sensation, tingling, itching or swelling. Rare side effects include an allergic reaction, which may manifest as dizziness or drowsiness.

IX. Potential Benefits

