Adverse Event (AE) is any untoward medical occurrence in a subject that does not necessarily have a causal relationship with this treatment. An AE can therefore be any unfavorable and unintended sign, symptom, or disease temporally associated with the use of an investigational product, whether or not related to the investigational product.

Serious Adverse Event (SAE) is any untoward medical occurrence that:

- Results in death
- Is life-threatening
- Requires inpatient hospitalization or prolongation of existing hospitalization
- Results in persistent or significant disability or incapacity
- Is a congenital anomaly/birth defect
- Is another medically important condition

Reporting and Documenting Adverse Events

All untoward medical occurrences that occur after the subject signs a consent form will be documented as an AE. The Investigator will ensure that all events that occur during the study period are recorded on an Adverse Events Tracking Log. We will report any adverse events that are experienced by subjects during their participation, even those determined to be unrelated to the study. All AEs will be followed until resolution or until, in the Investigator's judgment, they are chronic and stable. If an emergency situation should occur, appropriate medical measures should be taken to stabilize the subject.

Documentation of AEs includes: date and time of onset and resolution of AE, intensity, frequency, seriousness, related interventions and outcome. The Investigator will also evaluate the probability of a causal relationship of the AE to the study treatment as being: "definite, probable, possible, unlikely, or unrelated." Intensity of adverse events will be graded as mild, moderate, or severe according to the following criteria:

- Mild: symptoms that are easily tolerated and transient in nature with minimal or no impairment of normal activity
- Moderate: symptoms that are poorly tolerated, are sustained, and interfere with normal activity
- Severe: symptoms that are incapacitating and render the subject unable to work or participate in many or all usual activities

All SAEs will be reported to the IRB according to the IRB's requirements. They will also be reported to the study Sponsor.

Adverse events will be reported to the PHRC as described in the PHRC policy on Unanticipated Problems Involving Risks to Subjects or Others Including Adverse Events, which can be found on the Research Navigator website.

XII. Data Management

a. Data collection

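### Biopsies taken at the final visit have no scheduled safety follow-up, and that visit lists no adverse event evaluation

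*Combined protocol and SAP*

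**What the plan says.** **Biopsies.** Under Study Procedures, Skin biopsies: "Two skin biopsies will be obtained at visit 1 and at the post-procedural visit", one perilesional and one lesional each time, and "This will result in up to four biopsies per subject over the course of this study". The final-visit text repeats this: "Additional medical photography and two 3 mm-punch biopsies will be obtained, one from perilesional normal-appearing skin adjacent to treated lesion", with the second from lesional skin treated with laser. Both places make biopsies optional for scleroderma subjects only. Section V.c differs, because it describes the treated-side biopsy at the final visit as optional. Section II, Analysis of Skin Samples, also opens by calling the skin samples optional.

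**Last contact.** The post-procedural visit, one month after the third laser session, is labelled the final visit. No later visit, call or other contact is described. Biopsy sites are closed with absorbable sutures or gel foam, so no suture-removal visit is implied.

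**Biopsy risks.** Section VIII lists allergic reaction to the anesthetic, then "bleeding, infection, poor wound healing, pain, hyper or hypopigmentation and scarring".

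**Adverse event collection.** Section X.e says that untoward occurrences after consent are documented, and "We will report any adverse events that are experienced by subjects during their participation". Known events are followed until they resolve or are judged chronic and stable. No end of collection is given. Section X.b promises evaluation for adverse events throughout the study, without naming visits or sites.

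**Visit schedule.** Visits 2 and 3 each open with this line: "The treated lesion(s) will be evaluated clinically for any potential adverse events". The final visit has no such line.

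**The concern.** Infection, poor healing, pigment change and scarring at a punch site mostly show themselves in the days and weeks after the punch. For biopsies taken at the last contact, nothing in the plan prompts anyone to look or ask during that time. The rule on following events to resolution starts only once an event is known, so it does not find new ones.

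Two things are at stake. Biopsy-site events may be under-counted, in a branch enrolled for abnormal scar proliferation and with scarring among the stated biopsy risks. In addition, early and late biopsies would be observed for very different lengths of time, so a pooled count of biopsy-site events would be hard to interpret.

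The lesser concern is the third laser session. The final visit is the only one that follows it, and it is the one follow-up visit without an explicit adverse event evaluation.

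**Working it through.** **Inputs**
- Subjects: "Ten subjects with one or more hypertrophic scars and ten subjects with scleroderma will be recruited for this study" (Section V.c).
- Biopsies per subject: two at Visit 1 and two at the final visit (Study Procedures, Skin biopsies).
- Schedule: Visit 1, Visit 2, Visit 3 and the final visit, each one month apart.

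**Step 1: reproduce the plan's figure.** 2 + 2 = 4 biopsies per subject, which agrees with the stated maximum of four.

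**Step 2: scar branch, biopsies required as in the visit schedule.**
- Total: 10 × 4 = 40.
- Taken at the final visit: 10 × 2 = 20, and 20/40 = 50%.
- Scheduled contacts after the biopsy: three for the Visit 1 biopsies (about 3 months), none for the final-visit biopsies.

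**Step 3: scar branch, if the Section V.c wording governs.** If the treated-side biopsy at the final visit is optional and every scar subject declines it, 10 × 1 = 10 biopsies remain at that visit. The total becomes 20 + 10 = 30, and 10/30 = 33%. The range is therefore 10 of 30 to 20 of 40. On either reading, no biopsy taken at the final visit has a later scheduled contact.

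**Step 4: scleroderma branch.** If k subjects agree to all biopsies, 2k more are taken at the final visit. With k = 10 that is 20 more, so both branches together give 20 + 20 = 40 of 80.

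**Step 5: adverse event evaluation by visit.**

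| Visit | Follows laser session | Adverse event evaluation listed | Perilesional biopsy site named for it |
|---|---|---|---|
| 2 | 1 | Yes, treated lesion(s) | No |
| 3 | 2 | Yes, treated lesion(s) | No |
| Final | 3 | No; itch and pain questions, clinical scales or range of motion, photography | No |

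Two of the three laser sessions are followed by a visit that lists an adverse event evaluation.

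**Step 6: effect of one later contact.** Scar-branch biopsies followed by a scheduled contact rise from 20 of 40 to 40 of 40. If every scleroderma subject consents, the rise is from 40 of 80 to 80 of 80.

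**The case against.** **The adverse event window is open-ended.** Section X.e does not confine collection to the visits and sets no closing date. A subject who reports a biopsy-site infection a week after the final visit could have it logged and followed. This stands. It means that a late event can be recorded, but no scheduled step would bring it to light. The consent pages are not in the public file, so an instruction to report problems may exist there. Such an instruction would still leave the plan relying on unsolicited reports.

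**Some complications appear at once.** Allergic reaction to the anesthetic and early bleeding can be seen in clinic on the day. This also stands. The gap concerns the delayed complications.

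**The final visit is not without safety assessment.** The general clause in Section X.b applies to it. Subjects are asked about itch and pain, lesions are photographed, and the scar scale grades pliability, height, vascularity and pigmentation. Imaging may be done in selected subjects. Much of what could go wrong in a treated scar would be noticed this way. This largely answers the point about the third laser session and leaves an omission in a visit list. It does not reach the perilesional site by name or any date after the visit.

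**Scale.** These are 3 mm punches of a routine kind, subjects with a history of poor wound healing are excluded, and the sole stated aim is efficacy. That is fair, and it keeps the point modest. The remedy is correspondingly small.

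**Conclusion.** The point holds as a gap in scheduled safety ascertainment. Up to 20 of 40 scar-branch biopsies (10 of 30 if the treated-side biopsy at the final visit is optional and always declined), plus two for each fully consenting scleroderma subject, have no scheduled follow-up for delayed complications. The counts assume that all ten scar subjects complete the study. The missing evaluation line at the final visit and the unnamed perilesional site are lesser points.

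Three stronger readings are tempting, and the documents support none of them.
- A reader might infer that late biopsy events cannot be detected or recorded at all. Section X.e sets no end to collection, so self-reported events can be logged.
- A reader might take the inclusion criterion "Willing to sun protect treated area for the duration of enrollment in the study and 1 year after treatment" to imply a one-year safety window that the schedule fails to meet. It is an eligibility condition on willingness to take a precaution and sets no observation period.
- A reader might want an upper confidence limit for the biopsy complication rate. The plan has no such analysis, and paired sites in one subject cannot be assumed independent. The counts are the appropriate measure of size.

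The primary outcome, its test and the sample size of 10 per condition are not affected.

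**What to change.** 1. Add to the final visit the adverse event evaluation already listed at Visits 2 and 3, done before the biopsies. At Visits 2, 3 and final, name both the lesional and the perilesional biopsy sites as examined sites.
2. Add one remote contact by existing staff a few weeks after the final-visit biopsies, asking about events at the biopsy and laser sites. Define that contact as the end of scheduled adverse event collection.
3. Reconcile Section V.c and the opening of Analysis of Skin Samples in Section II with the final-visit and Skin biopsies text on which biopsies are optional and for whom.

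The cost is protocol and consent wording plus one short call for at most 20 subjects. The last subject leaves the study slightly later, and the adverse event count may look less favourable because more events are found. Treatment, endpoints and sample size do not change.
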